10.4 Medical Care of Subjects after End of Study

Not applicable. The subjects in this study are healthy volunteers.

10.5 Blinding

To guarantee double-blind conditions, the IMPs will be presented in identical liquid syrups, and the subjects will take the same dosage of syrup on all treatment days. The sample labels had no information that would allow identification of the treatment administered.

The randomization schedule will be guarded by the Pharmacy Department during the development of the study experimental phase. A separate randomization list will be generated for each cohort of the study (Cohort 1, Cohort 2, Cohort 3, Cohort 4 and Cohort 5) to allow each cohort of the study to be unblinded independently. Individual randomization envelopes will be delivered by the responsible of generating random list to the site before the beginning of the trial. These will be kept unopened in a secure place accessible to the investigator team.

With the exception of the Sponsor unblinding team (CEO and Project Manager), Pharmacy department, unblinded nurse responsible of IMP administration, the randomization manager, the DSMB members where necessary, PK analysis responsible (see Section 11.2) and Quality Assurance (QA) auditors where necessary, all clinical and non-clinical staff including the data management staff assigned to the study at the clinical unit and the Sponsor will remain blinded to treatment allocation until after the database is locked for that part of the study. Cohort 1, Cohort 2, Cohort 3 and Cohort 4 may be unblinded separately after the respective database for that part of the study has been locked.

Whenever the maintenance of the safety and well-being of the subject, as assessed by the investigator, requires the knowledge of the actually administered IMP, the investigator shall break the blind. In addition, in the case of unintended pregnancy of subject or the female partner of a subject participating in the study the investigator could break the blind. In case of any doubt, the investigator should contact the Sponsor to evaluate whether or not the blind should be broken. The investigators will report about this event to the Sponsor as soon as possible. If unblinding occurs, the investigator must record the reason for unblinding, as well as the date and time of the event. Corresponding information will be recorded on the eCRF and will be documented in a note to file which will be filed in the trial master file (TMF). Randomization codes will be controlled in the IRT system and procedures for breaking the codes in an emergency will be made available to relevant members of study site staff. Unless required by an emergency, the disclosure of the randomization list will be done after database lock.

The designated pharmacovigilance personnel will obtain the subject's treatment identity information only when there is a Suspected Unexpected Serious Adverse Reaction (SUSAR).

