10.2 Method of Assigning Subjects to Treatment Groups

At each investigated cohort, subjects will be randomized in the ratio of 6 active treatments to 2 placebos (3:1). For safety reasons, the subjects of each cohort will be divided in 2 sub-cohorts with 2 sentinel subjects in the first sub-cohort and 6 additional subjects in the second sub-cohort (see Section 8.1). The randomization schedule will be designed so that in each sub-cohort there will be 1 subject scheduled to receive placebo.

The randomization list will be performed by someone not directly enrolled in the research team. SAS software version 9.4 or higher will be used. The disclosure of the randomization schedule will be done at the end of the study or in case it is needed to provide convenient medical care to any subject due to AEs.

Following confirmation of eligibility, subjects will be assigned a subject randomization number at Baseline using an Interactive Response Technology (IRT) system in the order in which they are randomized in the study.

Only subjects receiving an IMP administration will receive a randomization number. Subjects who replace a discontinued subject will receive the same administration as the discontinued subject. This subject will receive a number that refers to the number of the subject that is being replaced.

In order to maintain the double-blind study, the administration of the IMP must occur individually and separately, and in the absence of the physician responsible for the study. This is because the reaction after its administration could be easily distinguishable between placebo and IMP.

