13. STATISTICAL METHODS AND DETERMINATION OF SAMPLE SIZE

13.1 Statistical and Analytical Plans

A separate statistical analysis plan (SAP), which will provide more details of the statistical analysis outlined below, will be prepared and approved prior to unblinding the study data. No formal statistical hypothesis of the safety or tolerability are to be tested for this study.

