13.4 Interim Analysis

The safety and tolerability data will be reviewed for each cohort during the DSMB meetings (see Section 8.1).

In addition, a Statistical Analysis has been conducted after completing Cohort 4 (2 mg/kg) and before enrolling subjects in Cohort 5 (4 mg/kg).

Date: 13 December 2023

Sponsor: Atlas Molecular Pharma S.L. Study Code: ATL001-PI-CEP Version: 4.0

NCT No.: 05647343

14. RESULTS FROM THE ANALYSIS REGARDING SAFETY AND EFFICACY OF COHORTS 1 TO 4 ARE AVAILABLE IN SECTION 6.3 OF THE IB.INVESTIGATOR/SPONSOR **RESPONSIBILITIES**

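### Protocol 10.2 and 10.5 set different times for revealing allocation, and 10.5 permits adverse-event assessors at the single site to know 32 of 40 allocations before they grade Cohort 5

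*Protocol*

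**What the plan says.** - **Protocol 10.2:** "The disclosure of the randomization schedule will be done at the end of the study", or when a subject's medical care requires it because of adverse events.
- **Protocol 10.5, lists and staff:** a separate randomization list is made per cohort "to allow each cohort of the study to be unblinded independently". Some roles are excepted from blinding: the Sponsor unblinding team, pharmacy, the nurse who gives the product, the randomization manager, the PK analyst and, where necessary, the DSMB and auditors. All other clinical-unit and Sponsor staff "will remain blinded to treatment allocation until after the database is locked for that part of the study".
- **Protocol 10.5, permission:** the sentence names Cohorts 1, 2 and 3 and ends "Cohort 4 may be unblinded separately after the respective database for that part of the study has been locked". Cohort 5 is not named.
- **Protocol 10.5, emergency text:** apart from emergencies, the list is disclosed after database lock. It does not say which lock.
- **Protocol 11.2:** concentrations are withheld from the site until the study, not the cohort, is unblinded.
- **Protocol 8.1 and 10.2, SAP 2.3.1:** doses are given individually and without the responsible physician present because, in the words of 10.2, "the reaction after its administration could be easily distinguishable between placebo and IMP".
- **Protocol 13.4, SAP 5.4.6:** an analysis was done after Cohort 4 and before Cohort 5 enrolment. The protocol adds that Cohort 1 to 4 results are in Section 6.3 of the Investigator's Brochure (IB). Neither document says whether the analysis was unblinded or who saw it.

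**The concern.** A reader of 10.2 would expect nobody at the site to hold allocations before the study ends, except for medical need. A reader of 10.5 would release them cohort by cohort. The difference matters more here than in most dose-escalation studies, because the protocol itself expects that active and placebo subjects might be told apart by their reaction. Staff who receive the codes of finished cohorts can look back and learn which reactions went with the drug.

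Cohort 5, at the highest planned dose, would then be assessed by people who may recognise active subjects. At stake are the judgements that depend on the assessor: the related TEAEs (SAP 4.5.2), the AESI, which are gastrointestinal events judged related (Protocol 12.5), the stopping rule for a possibly related SAE (8.1.2), and the DLT exception for a clear-cut alternative explanation (8.1.3).

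**Working it through.** **1. The disclosure rules side by side**

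| Place | When allocation is released | To whom |
|---|---|---|
| Protocol 10.2 | End of study, or medical need | Not stated |
| Protocol 10.5, main rule | Lock of that part of the study | All staff not already excepted |
| Protocol 10.5, permission | Each of Cohorts 1 to 4 after its own lock | Not restricted |
| Protocol 10.5, emergency text | After database lock, unspecified | Not stated |
| Protocol 11.2 (concentrations) | When the study is unblinded | Site and blinded personnel |

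The second and third rows conflict with the first. The fourth row fits either rule. The fifth points towards study-level blinding but concerns concentrations only. No row makes release wait for later cohorts or keeps codes from adverse-event assessors. The amendment summary lists 10.5 among the sections updated in version 4.0, which added Cohort 5, so the section was looked at when that cohort was planned.

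**2. How many allocations.** Inputs are five cohorts of 8, with 6 active and 2 placebo each (Protocol 8.1, 13.2).

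- Whole study: 5 × 8 = 40, which reproduces the protocol's figure; 5 × 6 = 30 active and 5 × 2 = 10 placebo.
- Cohorts 1 to 4: 4 × 6 = 24 active, 4 × 2 = 8 placebo, 24 + 8 = 32.
- Share: 32 / 40 = 80%.

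This is the most that 10.5 permits, reached if all four databases are locked and opened before Cohort 5 is graded. Lock dates are not given.

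**3. Could it happen in time?** For Cohort 5, 13.4 places the Cohort 1 to 4 analysis before enrolment. Overlap was also possible earlier, because the next cohort waits for FU-V1 data and not for a database lock. Assume the fastest pace, with each step starting the day after the preceding FU-V1 and lock no earlier than FU-V2. Count from Cohort 1's first dose as day 0:

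- Sentinels are dosed on days 0 to 4, with FU-V1 on day 7. The second sub-cohort is dosed on days 8 to 12, with FU-V1 on day 12 + 3 = 15 and FU-V2 on day 12 + 30 = 42.
- Each cohort starts 16 days after the one before, so Cohort 3 doses on days 32 to 44. Cohort 1's earliest lock, day 42, falls inside that span.

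**4. What the old codes add.** They tell an assessor how often the reaction occurs on active (p) and on placebo (q). With 6 of 8 active, the starting probability is 0.75, and

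P(active | reaction) = 0.75p / (0.75p + 0.25q).

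The documents give no p or q. Assuming q = 0.10:

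- p = 0.50: 0.375 / (0.375 + 0.025) = 0.94; with no reaction, 0.375 / (0.375 + 0.225) = 0.63.
- p = 0.90: 0.675 / (0.675 + 0.025) = 0.96; with no reaction, 0.075 / (0.075 + 0.225) = 0.25.

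This shows the mechanism only. The design adds to it: each sub-cohort holds exactly one placebo subject, so recognising one sentinel's arm reveals the other's, and recognising the placebo subject in the second sub-cohort reveals all five active subjects.

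**5. Does the safeguard cover it?** The physician is absent at administration. The 2-hour and 24-hour examinations, adverse-event questioning and follow-up visits come later and are not covered.

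**The case against.** **A lenient reading.** 10.2 could be taken to mean the full schedule and 10.5 the cohort lists. But 10.2 makes no cohort-level exception, and a site could follow either section and claim compliance.

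**Permission, not event.** 10.5 says that cohorts may be unblinded, and only after lock. Separate lists mean that Cohort 1 to 4 codes disclose no Cohort 5 allocation. That the same staff assess every cohort is inferred from the single site. All of this stands. A reader might infer that assessors were unblinded; the documents do not show it.

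**The reaction is hedged.** The protocol says that it could be distinguishable, not that it is, and never says what it consists of or that it resembles the events graded later. This stands.

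**The fix may gain little.** If reactions are obvious, assessors need no codes; if they are not, old codes teach little. This has force at the two extremes. Between them, codes help most. The IB route for aggregate results stays open either way.

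**The primary endpoint is less exposed.** It is the incidence of adverse events and clinically relevant changes, whatever their cause. Grading follows CTCAE, all-causality TEAE tables are planned, and the DLT criterion on grade 2 or higher events does not require relatedness. The analyses are descriptive. This moves the weight from incidence and grading to causality.

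**Two stronger readings fail.** A reader might infer that SAP versions 2.0 (11-Mar-2024) and 2.1 (26-Apr-2024) break the promise in 13.1 that the SAP "will be prepared and approved prior to unblinding the study data". Version 1.0 is dated 09-Aug-2023, before Protocol 4.0 (13 December 2023) reported the analysis as done, and the analysis date is not given, so no breach is shown. A reader might also attach a several-fold spurious excess of related events to Cohort 5. The documents supply no attribution rates, and SAP 4.1 pools all placebo subjects, 8 of 10 from Cohorts 1 to 4. A ratio that treats every placebo subject as recognised would not describe the planned comparison.

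**Conclusion.** The point holds as a conflict of rules with an avoidable risk of bias, not as a documented failure of blinding. Its measurable size is 32 of 40 allocations (80%) that 10.5 permits assessors to know before Cohort 5 is graded. The effect on results cannot be quantified from the documents.

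The risk rests on three assumptions: that site staff would actually be given the codes, that assessors overlap across cohorts, and that the reaction is at least partly recognisable. If they hold, causality in Cohort 5 is exposed first (related TEAEs, AESI, the SAE stopping rule), with the DLT exception. Grading is exposed to a lesser extent. If cohorts were opened one at a time, later assessments within Cohorts 1 to 4 could be affected too. Because the remedy costs so little, the sections should be reconciled even though no harm is shown.

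**What to change.** **Protocol 10.2 and both parts of 10.5: one rule.** Until the Cohort 5 database is locked, subject-level allocation of completed cohorts goes only to the roles already listed as unblinded in 10.5 and to the analysts of the Cohort 1 to 4 report. The investigator and site staff who record, grade or attribute adverse events stay blinded to all cohorts. Emergency and other individual code-break provisions stay as they are.

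**SAP 5.4.6.** State whether the Cohort 1 to 4 analysis was unblinded and who saw it. If any adverse-event assessor was unblinded, report this as a limitation of the Cohort 5 causality results and lead with the all-causality TEAE tables already planned. This part can still be done if Cohort 5 has already been assessed.

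**Cost.** A sentence or two in the protocol and a few lines in the SAP, with no added subjects, procedures or visits. Site staff wait until the final lock for individual allocations. Aggregate results still reach them through the IB, so the rule reduces the risk but does not remove it.

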10.6 Prior and Concomitant Therapy

Prior medications are defined as all medications taken within 8 weeks prior to the Screening Visit (whether continuing or not). The use of all medication taken by the subject must be recorded in the appropriate sections of the eCRF.

10.6.1 Permitted Medications

No concomitant medications will be allowed during the treatment period of the study.

If considered necessary for the subject safety and well-being, concomitant medication may be given at the discretion of the Investigator. However, concomitant medication administered during the study may lead to withdrawal of the subject from the study (see Section 9.4). Decisions regarding replacements of subjects requiring concomitant medications will be discussed with the Sponsor on a case by case basis.

10.6.2 Prohibited Medications

All concomitant medications will be forbidden during the treatment period of the study. Specifically, the following medications will be prohibited:

Date: 13 December 2023

Sponsor: Atlas Molecular Pharma S.L. Study Code: ATL001-PI-CEP

NCT No.: 05647343

- Medications that interfere with the glucuronidation metabolic pathway
- Antineoplastic or anticancer drugs

10.7 Treatment Compliance

All IMP administrations will be daily recorded by the subject in the subject diary, ensuring treatment compliance for all subjects. The two firsts and last administrations of the IMP (Day 1 and Day 5) will be performed at the hospital.

If an administration is omitted for any reason, the continuation of the IMP or possible withdrawal of the subject will be discussed with Sponsor and decided on a case-by-case basis.

10.8 Drug Accountability

In accordance with GCP, the unblinded team member at each Investigational Sites will account for all supplies of the IMPs. Details of receipt, storage, assembly and return will be recorded. The precise amount of medication administered to each subject has to be documented in the subject's medical records, eCRF for each subject and study drug accountability records.

All unused supplies of the IMPs will either be destroyed or returned to the Sponsor at the end of the study in accordance with instruction by the Sponsor. If destroyed locally, a certificate of destruction must be provided to the Sponsor.

The unblinded team member should keep the used vials and only discard them after the Drug Accountability.

Version: 4.0

Date: 13 December 2023

Sponsor: Atlas Molecular Pharma S.L. Study Code: ATL001-PI-CEP

NCT No.: 05647343

11. STUDY ASSESSMENTS

11.1 Efficacy Assessments

This is a Phase I study in healthy subjects. The efficacy of the IMP will not be tested.

11.2 Pharmacokinetic Assessments

Drug concentration information that may unblind the study will not be reported to the investigational site or blinded personnel until the study has been unblinded. Drug concentrations will, however, be disclosed to the PK analysis responsible person after completion of each cohort for PK model parameter estimation and simulation of plasma profiles of the subsequent cohort. The PK analysis responsible person will simulate plasma concentration profiles with variability of ATL-001 for the proposed dose of the next cohort. The timing of the plasma concentration reporting, the modelling and the simulation will be such that the DSMB meetings can be informed while the overall timelines of the study will not be jeopardized.

11.2.1 Sampling Procedures

Blood samples will be collected at specific time points throughout the study. The maximum amount of blood to be collected for PK analyses along the study is 5 mL in each extraction point. For each day when a PK sampling is collected a total amount 60 mL of blood (12 points) will be withdrawn.

The timing of the sampling is described in Section 8.2.1 and Table 1.

Details on collection, storage and handling of blood samples will be included in the respective Laboratory Manual.

11.2.2 Bioanalytical Method

The bioanalytical analysis will be performed by Covance Labcorp using approved bioanalytical methodology. Raw data will be archived in the Labcorp archives.

11.2.3 Definition and Calculation of Pharmacokinetic Parameters

The following PK parameters will be derived from each individual plasma concentration versus time profile using standard methods if the data warrant doing so (Table 11).

Table 11. Pharmacokinetic Parameters to be Analyzed

Parameter	Definition	
C _{max}	Maximum observed plasma concentration	
t _{max}	Time until C _{max} is reached	
AUC (0-last)	AUC from time 0 to the time of the last measured concentration	
AUC (0-12)	(0-12) AUC from time 0 to 12 hours after drug administration	
AUC (0-24)	AUC from time 0 to 24 hours after drug administration	
t _{1/2}	Plasma concentration half-life	
CL/F	Apparent total body clearance	
Vz/F	Apparent volume of distribution	

Version: 4.0 Date: 13 December 2023 Sponsor: Atlas Molecular Pharma S.L. Study Code: ATL001-PI-CEP

NCT No.: 05647343

11.3 Demographic and Other Baseline Characteristics

11.3.1 Demographic and Baseline Data

The following demographic and baseline data will be collected at the Screening Visit:

- Age
- Sex
- Race
- Weight (for dose calculation from Day 1 to 5)
- Height
- BMI calculated

11.3.2 Medical History

Past (within 6 months prior to screening visit) or current medical conditions judged relevant by the investigator including general, head and neck, eyes, throat, chest/respiratory, heart/cardiovascular, gastrointestinal/liver, gynecological/urogenital, musculoskeletal/extremities, skin, neurological, endocrine/metabolic, hematologic/lymphatic, allergies/drug sensitivities, past surgeries, substance abuse or any other diseases or disorders.

The timing of the sampling is described in Section 8.2.1 and Table 1.

11.3.3 Prior and Concomitant Medication

Prior medications taken within 8 weeks prior to screening will be recorded at the Screening visit.

Concomitant medication will be recorded on the concomitant medication log/page of the eCRF throughout the study.

11.4 Safety Assessments

11.4.1 Safety Variables

The following safety variables will be measured:

- AEs
- Physical examination
- Vital signs
- ECG
- Laboratory safety assessments (including viral serology and drugs of abuse, and alcohol screen)

11.4.2 Adverse Events

AEs will be recorded during the study period from the informed consent signatory to the completion of the FU-V2 (30 days after the last IMP dose). For further information of definitions and reporting of AEs and SAEs, see Section 12 below.

11.4.3 Physical Examination

All subjects will undergo a standard physical examination. General physical examinations will include the following body systems: heart, lung, abdomen, nervous system, skin, musculoskeletal system, lymph nodes, limbs, head, ears, eyes, nose, throat, and others.

The examinations will be recorded and assessed as "normal" or "abnormal". Abnormal findings will be assessed as "clinically significant" or "not clinically significant".

The timing of the assessments is described in Section 8.2.1 and Table 1.

Version: 4.0

Date: 13 December 2023

Sponsor: Atlas Molecular Pharma S.L.

Study Code: ATL001-PI-CEP

NCT No.: 05647343

11.4.4 Vital Signs

The following vital signs will be monitored as safety variables:

- Resting systolic and diastolic blood pressure (mmHg), after 5 minutes sitting
- Resting pulse rate (beats per minute), after 5 minutes sitting
- Axillary body temperature (°C)

Additional vital signs may be monitored for the safety of the subjects.

The observed values will be recorded and assessed as "normal" or "abnormal". Abnormal findings will be assessed as "clinically significant" or "not clinically significant".

The Investigator may choose to repeat any abnormal result once, in order to rule out measurement error. Clinically relevant deviations of vital signs results occurring during or at post-study examination must be reported and discussed with the Sponsor, if applicable. Repeated measurements are mandatory until their normalization or until the time course and reason of the underlying process can clearly be assessed positively.

The timing of the assessments is described in Section 8.2.1 and Table 1.

11.4.5 Electrocardiogram

A standard 12-lead ECG will be performed by authorized site staff after the subject has been calmly resting in a supine position for a minimum of 5 minutes before obtaining the ECG. ECGs should precede measurement of vital signs and blood draw for clinical laboratory tests.

ECG findings will be recorded and assessed as "normal" or "abnormal". Abnormal findings will be assessed as "clinically significant" or "not clinically significant".

The timing of the assessments is described in Section 8.2.1 and Table 1.

